Aim 1: In a multi-site, two-armed randomized trial of older drivers (n=300;  $\geq$ 70 years) and family members, to test the effect of a web-based DDA as compared to control (web-based information only on:

1a. Immediate decision quality (measured by the Decisional Conflict Scale), hypothesizing that more DDA participants will make high-quality decisions;

1b. Longitudinal psychosocial outcomes at 12 and 24 months, hypothesizing that DDA participants will have reduced prevalence of depressive symptoms and of decision regret but maintained life space

1c. Longitudinal driving behaviors (including reduction or cessation) at 12 and 24 months, hypothesizing that the DDA- although not intended to direct participants to continue or stop driving- will lead to changes.

Aim 2: Using data from Aim 1, to use stratified analyses to determine the DDA's effects in specific subpopulations, including:

2a. Older drivers with versus without cognitive impairment, hypothesizing that the DDA will improve decision quality more in cognitively intact drivers;

2b. Older drivers with maintained versus impaired decisional capacity, hypothesizing that the DDA will improve decision quality more in drivers with maintained decisional capacity;

2c. Older drivers who are attitudinally more ready versus less ready for a mobility transition, hypothesizing that the DDA will improve decision quality more in drivers who are ready for transition.

Aim 3: Through qualitative interviews and surveys with key stakeholders (older drivers, family members, healthcare providers, and experts in the field), to identify the desirable settings for DDA use, including:

3a. acceptability and suggestions for modifications or targeted use with subpopulations;

3b. preferred locations, such as clinical settings, community programs, or at home.

The proposed study will provide the groundwork for tailoring intervention delivery and preparing for its implementation.

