## **Background and Significance:**

"Driving retirement" is a critical life decision. As of 2015, there were over 25 million drivers aged  $\geq$ 70 years, and 70% of adults aged  $\geq$ 85 years still had a driver's license. Driving is closely linked to well-being, and driving retirement can negatively impact independence and mental health. A recognized national goal, therefore, is to help older drivers stay on the road as long as it is safe, as maintaining mobility and community involvement promotes health and longevity. Safety remains a consideration since some older drivers are at increased risk of crashes and fatal crash rates increase after age 75, but generally older drivers pose a greater risk to themselves than to the community around them. Precise estimation of an individual driver's risk remains difficult, as on-road testing is costly and not always available and office-based assessment is often impractical and not routine. Thus, decisions about driving retirement typically involve some combination of the older driver, involved family members or trusted friends, and healthcare providers, depending on the individual's circumstances and preferences.

Decision-making is a multi-dimensional process. Decisions are affected by complex interactions between myriad internal and external factors, including cognitive ability, decisional capacity, emotions, personality, and environmental or pragmatic factors. Older drivers fear losing their

COMIRB No: 19-0059

independence, being abandoned, or becoming a burden on others, while simultaneously fearing causing harm to others on the road, and decisions about driving are complicated by financial and lifestyle considerations, such as alternative transportation options. The mechanisms of decision-making also change over an individual's life, and the process can be further complicated by attitudinal factors (e.g., emotional readiness for a major transition) and cognitive function. Understanding how key attitudinal and cognitive factors affect decisions about driving gains critical urgency with the aging population in the US who rely heavily on driving themselves.

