Analysis for Aim 1: Analyses will be performed according to the principle of intention-to-treat. including all randomized drivers. Unless otherwise specified, hypothesis tests will be two-sided with alpha=.05, with 95% confidence intervals or p values reported. All canalyses will be performed using SAS/STAT® software. First, descriptive statistics will be computed for baseline patient characteristics, initially testing for differences between control and intervention groups (including for key covariates, Table 3.3). We will assess site effects by comparing demographic variables across the sites, using ANOVA for continuous measures and chi-square tests of proportions for categorical measures. If no statistically significant differences exist among sites. we will ignore site and formally test the differences in proportions or means as described below. If there are significant differences among sites, then (assuming enough events) we will use separate bivariate logistic regression models for each aim described below, with a fixed effect for site and with treatment arm as the main predictor. For longitudinal analyses, we will conduct logistic regression with unstructured correlation of generalized estimating equations (GEE) to account for the repeated observations for each participant. Statistical significance will be evaluated at one-sided p<.05 level. Analyses of the DDA's longitudinal effects may be vulnerable to bias, as control arm participants may be exposed to intervention arm messages through exposure to available materials or courses related to driving safety or cessation (e.g., websites, physician counseling, AARP courses). We will assess exposure to other sources of information through structured questions. To mitigate the impact of this potential bias, we will adjust measurements of contamination as applicable. In all analyses, validation of distributional and parameterization assumptions will be checked and data transformations (e.g. logtransformations) or alternative methods will be implemented as appropriate.

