Aim 1b. Test the DDA's longitudinal effect on psychosocial outcomes at 12 and 24 months. Hypothesis 1b: Participants in the DDA group will have reduced prevalence of depressive symptoms and of decision regret but maintained life space, at 12 and 24 months after enrollment, compared to control participants. We will use descriptive statistics, including proportions with 95% CIs or medians and interquartile ranges, for comparison between treatment groups. We will utilize GEE with a linear link, and a linear mixed model (LMM) with a random intercept, fixed effects and a linear link for each outcome. We will adjust for baseline characteristics (gender, age, education, etc.), driving behaviors and other variables. We will perform sensitivity analyses to examine the missing assumption under maximum likelihood.

Aim 1c. Test the DDA's longitudinal effect on driving behaviors at 12 and 24 months. Exploratory: The DDA does not provide specific recommendations as to whether the participant should stop driving or not. We will compare the proportion of participants who change their reported driving behaviors (reduce driving or cease altogether) over the follow-up period to examine whether the DDA appears to affect them. We will apply GEE with a logistic link, and a generalized LMM (GLMM) with a random intercept and a logistic link for each outcome. Also, we will adjust demographic variables and appropriate variables.

Secondary analyses: Secondary analyses by gender will be conducted, as we hypothesize there will be differences in behavior and outcomes based on gender, and the belief that the responses to DDA intervention may be heterogeneous between men and women. Aim 1a-1c will be considered gender analyses using logistic regression and GLMM. We will also examine the degree of concordance (or discordance) within driver-family dyads on various measures, including DCS and current versus desired level of family involvement in driving retirement process (part of the driving questionnaire). For longitudinal data, we will examine changes across time points (follow-up at 6, 12, 18, 24 months) and correlation between older driver and family member report.

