#### **Description, Risks and Justification of Procedures**

#### **Risks to Human Subjects:**

This is a minimal risk study. One risk of this study is loss of privacy due to breach of confidentiality. We will make every attempt to keep information private. Screening logs will not contain any identifying information. To ensure adequate protection of confidentiality, any age above 89 will be treated as an identifier and will be recorded as 89+ in screening logs. Data will be stored in a secure, password protected database on the University of Colorado server, (or equivalent institutional servers at other sites), with access limited to study personnel. Some participants may be uncomfortable discussing driving. They may choose not to answer certain questions. The research team will report any activities resulting in participant discomfort or injury to the IRB immediately.

Older adult drivers will be asked questions related to their driving behavior in addition to measures related to physical health, cognitive impairment, and decision-making capability. Mandatory reporting of potential driver impairment due to medical conditions varies by state. Of note, in this study we will not be assessing actual driving function, and no single question or cognitive test is accurate in identifying driving risk. Driving cessation itself comes with risks, so the study team will not automatically report drivers with particular MoCA scores. However, during the informed consent process, we will explain the study protocol related to participants who have clear visual, cognitive or functional deficits suggesting a driving safety concern, and individuals must agree to the protocol in order to enroll. In identifying potential impairment, research staff will draw upon evidence and impressions from responses as well as participant observation; examples might include a participant who is unable to remember the question just asked, who is disoriented to the purpose of the questions, who mentions a diagnosis of cognitive impairment/dementia or new difficulties with memory, who mentions new significant

AUTO Study Protocol: Version Date: 12/22/21

PI: [name], MPH COMIRB No: 19-0059

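### An unexplained one-sided p<.05 rule, apparently for the longitudinal tests, overrides the two-sided default: it doubles the false-benefit rate for depression and regret and is ill-defined for life space and driving behaviour

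*Combined protocol and SAP*

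**What the plan says.** All of this is in the combined protocol and SAP. Under Outcome Measures and Analysis, the Analysis for Aim 1 paragraph opens with a default: "Unless otherwise specified, hypothesis tests will be two-sided with alpha=.05". It asks for 95% confidence intervals or p values. Later in the same paragraph comes "For longitudinal analyses, we will conduct logistic regression with unstructured correlation", fitted by GEE, and the next sentence is "Statistical significance will be evaluated at one-sided p<.05 level". That sentence names no aim, no outcome and no direction, and no reason is given there or elsewhere.

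The Aim 1b and Aim 1c paragraphs do not mention one-sided testing. Hypothesis 1b expects "reduced prevalence of depressive symptoms and of decision regret but maintained life space" in the DDA group compared with control at 12 and 24 months, and the Aim 1b text plans proportions with 95% intervals. Aim 1c is labelled exploratory. It notes that the DDA makes no recommendation for or against stopping, and compares changes in driving "to examine whether the DDA appears to affect them". The Specific Aims say of Aim 1c that the DDA, "although not intended to direct participants to continue or stop driving- will lead to changes".

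The Sample Size section gives 90% power at a 0.05 level for the primary Aim 1a comparison, without saying whether the test is one- or two-sided. It gives no power for Aims 1b or 1c.

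**The concern.** A one-sided test needs a direction fixed in advance and a reason for treating the other direction as uninteresting. The plan gives no reason, and it gives a clear direction for only some of the outcomes that the rule appears to cover.

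- **Depressive symptoms and decision regret.** The direction is a reduction. The bar for claiming benefit is lower than under the default, and an increase cannot be declared significant however large it is. The protocol gives grounds for caring about an increase: Aim 1c expects driving to change, the Background says "driving retirement can negatively impact independence and mental health", and the risk section says "Driving cessation itself comes with risks". These passages concern stopping driving in general, not an effect of the DDA, but they are enough to make the unfavourable direction worth testing.
- **Life space.** Maintained compared with control, with no margin, could mean superiority, non-inferiority or no difference.
- **Driving behaviour (Aim 1c).** More reduction or cessation under the DDA can be inferred, because the outcome is reducing or stopping. The stated question is only whether driving is affected, and neither direction counts as favouring the DDA.

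At stake are the longitudinal claims: Aim 1b, whose outcomes Table 3 lists as secondary, and the exploratory Aim 1c.

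**Working it through.** **1. Which tests does the sentence cover?** The plan's own figure helps here. Inputs from Sample Size: 150 per arm, 10% loss (150 × 0.90 = 135 per arm), a difference of at least 20 points, 90% power, level 0.05. The underlying proportions are not in the text, so 40% v 60% is assumed, the least favourable 20-point pair.

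Power = Φ[(0.20 − z·SE0)/SE1], with SE0 = √(2 × 0.5 × 0.5/135) = 0.0609 and SE1 = √((0.24 + 0.24)/135) = 0.0596.

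- Two-sided, z = 1.960: (0.200 − 0.1193)/0.0596 = 1.35, power 91%.
- One-sided, z = 1.645: (0.200 − 0.1001)/0.0596 = 1.68, power 95%.

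Solving for 90% power gives 130 per arm two-sided (145 after loss) and 106 one-sided (118 after loss). The planned 150 fits a two-sided primary test better. This supports reading the one-sided sentence as longitudinal only, but does not prove it.

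**2. Error rates per test.** These need no trial inputs.

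- Two-sided .05: z = 1.960, false claim in a given direction 1 − Φ(1.960) = 2.5%.
- One-sided .05: z = 1.645, false claim in the tested direction 1 − Φ(1.645) = 5.0%, the same bar as two-sided p < .10. The matching interval is 90%, not the 95% that the plan reports.
- Direction fixed in advance: total type I error stays 5%. Direction chosen after seeing the data: 5% + 5% = 10%.

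**3. Size of the gap (illustration).** Table 3 scores depression for Hypothesis 1b as T-score >50. Assume 135 per arm, one time point, an unadjusted pooled two-proportion z-test, and control prevalence of 20% to 50% (not in the documents). The smallest significant reduction, in percentage points, is:

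| Control prevalence | One-sided .05 | Two-sided .05 |
|---|---|---|
| 20% | 7.4 | 8.7 |
| 30% | 8.7 | 10.3 |
| 40% | 9.6 | 11.3 |
| 50% | 10.0 | 11.8 |

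Example: 54/135 (40.0%) in control v 40/135 (29.6%) with the DDA. The difference is −10.4 points. The pooled proportion is 94/270 = 0.348, SE = √(2 × 0.348 × 0.652/135) = 0.0580, and z = 0.1037/0.0580 = 1.79. One-sided p = .037; two-sided p = .074. The unpooled SE is √(0.400 × 0.600/135 + 0.296 × 0.704/135) = 0.0576, so the 95% interval is −10.4 ± 1.960 × 5.76, or −21.7 to +0.9 points. The rule says significant; the interval includes no effect.

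On the mean T-score scale, taking SD 10 from the T-score standardisation rather than from trial data: SE = 10 × √(2/135) = 1.217. The thresholds are 1.645 × 1.217 = 2.0 and 1.960 × 1.217 = 2.4 points.

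**4. The unfavourable direction.** With control at 40% and a true rise to 57% under the DDA (a rise picked to give 80% power), a two-sided test is significant in about 80% of trials. A one-sided test for a reduction never declares a rise significant, whatever its size.

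**5. Power given up by the fix.** An effect with 80% power one-sided has shift 1.645 + 0.842 = 2.487. Two-sided power is then Φ(2.487 − 1.960) = Φ(0.527) = 70%. For 90%: 1.645 + 1.282 = 2.927, and Φ(0.967) = 83%.

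**The case against.** The strongest reply is that the default expressly allows exceptions and this sentence makes one. A planned one-sided .05 test in a fixed direction holds type I error at 5%. For depression and regret the direction is stated, and the protocol supports it: its overarching hypothesis is that better decisions soften the psychosocial cost of driving less, and its Background cites a review in which decision aids improved regret. Only secondary and exploratory outcomes are involved. The illustrative band is 1.3 to 1.9 points wide on assumed inputs; the 10% loss belongs to the Aim 1a calculation, and the planned models are adjusted and use repeated measures.

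Much of that stands, and it rules out several stronger readings that a reader might infer:

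- *The paragraph contradicts itself.* Formally it does not, because exceptions are allowed. The defect is an exception with no reason and an incomplete definition.
- *No direction is stated anywhere.* Not so for depressive symptoms and regret.
- *The primary test is one-sided.* The sentence order and the sample-size figure point the other way. The sentence names no aim, however, so this cannot be excluded from the text. If it did cover all of Aim 1, it would reach the primary test and leave the default with nothing to govern in that aim. Its reach to Aim 1b is also inferred, since the preceding sentence describes logistic GEE while Aim 1b plans linear-link models.
- *Type I error is 10%.* Only if the direction were picked after seeing the data, and nothing suggests that this is intended.
- *Harm would be hidden.* An interval would show it; it simply could not be called significant.

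What the reply does not answer is the missing reason, the mismatch with 95% intervals, and the lack of a clear test direction for life space and Aim 1c.

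**Conclusion.** The point holds as a moderate defect that should be fixed before analysis. On the natural reading it affects Aims 1b and 1c and leaves the primary Aim 1a test two-sided.

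For depressive symptoms and decision regret, the doubling from 2.5% to 5% per test is exact, as is the inability to declare a worsening significant; both follow from the stated direction. For life space and Aim 1c the rule cannot be applied without first deciding which direction is tested, and the plan does not clearly say.

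Two things rest on inference or assumption: the scope of the sentence, which is read from its position, and the prevalence and T-score figures, which only illustrate scale. The real gaps under the planned adjusted, repeated-measures models would differ.

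**What to change.** Replace the one-sided sentence in Analysis for Aim 1 with: *All Aim 1 hypothesis tests, immediate and longitudinal, are two-sided at alpha=.05 and reported with 95% CIs.* This settles the scope, removes the need to define a direction for life space and Aim 1c, and makes decisions agree with the intervals.

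Tightening to one-sided .025 instead is not enough. It would restore the 2.5% false-benefit rate, but would still leave worse depression or regret impossible to declare significant.

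The cost is one sentence, with no change to sample size or data collection. The longitudinal tests lose nominal power as shown in step 5 of the working; because the plan states no power for Aims 1b and 1c, no stated claim is broken.

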## AUTO Study Protocol: Version Date: 12/22/21 PI: [name], MPH COMIRB No: 19-0059 **Table 3. Key study measures**. Shown in relation to measurement point (pre- or post- DDA or website

Participant, and analytic plan. • = about self,  $\circ$  = as surrogate about older driver

		[name]/friends			Analytic Plan				
Domaiı	n and Key Measures	En	roll	F/u	Enr	oll	F/u			
		Pref	Post		Pre	Post			Hypoth.	Scoring
Immediate outcome										
Decision Conflict	Decisional Conflict Scale (DCS)	•	•	•	٠	•	•	1° Outcome	1a, 2a, 2b, 2c	Score <25
Knowledge	Knowledge questionnaire	•	•	•		•	•	2° Outcome	1a	Descriptive (cat.)
Values concordance	DCS Values Clarity subscale	٠	٠	•	٠	٠	٠	2° Outcome	1a	Descriptive (cat.)
Self-efficacy	Decision Self-Efficacy scale	•	•	•		•	•	2° Outcome	1a	Descriptive (contin.)
Longitudinal outcome										
Depression	PROMIS depression	٠		٠				2°	1b	T-score >50
								Covariate	1c	Descriptive (contin.)
Decision regret	Ottawa Decision Regret Scale			•			•	2° Outcome	1b	Descriptive (contin.)
Life space	Life-Space Assessment	٠		•			0	2° Outcome	1b	Descriptive (contin.)
Driving behaviors	Amount; reduction or cessation	•		•			0	2° Outcome	1c	Descriptive (cat.)
Subgroups										
Cognitive	5 minute MoCA			٠			•	Eligibility		Score ≥21
screening								Covariate	•	
Cognitive function	BTACT, OTMT	•						Stratify	2a	Normal vs. impaired
Insight	Beck Cognitive Insight Scale	٠		٠				Stratify	2a	R-C index ≥3
Decisional capacity	SPACED	•		•				Stratify	2b	# correct answers
Attitudes about	ARMT	٠		٠				Stratify	2c	Mean score ≥3.57
anning								Covariate	1c	_0.07

	Drivers	Family/fri	Analytic Plan				
Domaii	n and Key Measures	Enroll F	/u Enroll	F/u			
		PrePost	Pre Post			Hypoth.	Scoring
Other covariates							
Demographics	E.g., age, gender, race/ethnicity, marital/home status, education, income, urban/rural	•	• •	•	Covariate	all	Descriptive (cat.)
Physical health	Medical history, Activities of Daily Living, PROMIS global health	•	•	•	Covariate	all	Descriptive (cat.)
Mental health	PROMIS Emotional Support, Social Isolation; Perceived Stress Scale	•	•		Covariate	1b, 1c	Descriptive (cat.)
Personality	TIPI	•			Covariate	1c, 2c	Descriptive. (cat.)
Driving behaviors	Crashes, self-driving technologies	•	•	0	Covariate	1c	Descriptive (cat.)
Driving resources	Alternative transportation, support	•	••	• 0	Covariate	1c	Descriptive (cat.)
Driving education	Use of websites, courses, or other material driving or cessation	•	• •	•	Covariate	1c	Descriptive (cat.)

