Family questionnaire	Relationship to driver, co- reliance		•	•	Covariate	1a	Descriptive (cat.)
Life Events	Major Life Events		•	•0	Covariate	all	Descriptive (cat.)
Coronavirus- related health	Coronavirus/COVID-19 Health/Exposure Status	•	• •	•			

Subgroups: Analyses will include stratification by cognitive and attitudinal factors.

-Cognitive function: At baseline we will administer the Brief Test of Adult Cognition by Telephone, which assesses episodic memory (word list recall immediate and delayed), Category verbal fluency, Backward digit span, 30-Second Counting task, Number series, Stop & GoSwitch Task, and Executive Functioning. We will augment the BTACT with the Oral Trail Making Test (OTMT). [name] will categorize participants' cognitive function as MCI, dementia or non-impaired based on the BTACT Composite and OTMT-B (z-score < -1.5 is impaired). [Note: initial study protocol included RBANS and TMT instead of BTACT and OTMT; see protocol version 10.14.19 for more details]

-Insight: The Beck Cognitive Insight Scale comprises two sub-scales (self-reflectiveness and self-certainty); the composite "R-C index" (self-reflectiveness score minus self-certainty score) reflects overall cognitive insight. In one study each sub-scale and the R-C index were lower in

AUTO Study Protocol: Version Date: 12/22/21 PI: [name], MPH COMIRB No: 19-0059 those with probable Alzheimer's disease compared to control. We will use a conservative cutoff, with <3 categorized as low insight.

-Decisional capacity: This construct is related to but distinct from cognitive ability. We will use the Short Portable ACED (SPACED) to measure understanding, appreciation, comparative reasoning, and consequential reasoning. Each of these four criteria are scored a 0 for inadequate, 1 for marginal, and 2 for adequate. This produces as total range of 0 to 8. In the end, participants can be dichotomized as those with 0s versus others, median split, 8's versus others, etc. Scores can also be used as a continuous outcome measure in regression models...

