-Driving education: To assess possible control group contamination, at baseline and follow-up we will assess exposure to websites, videos, courses, or other educational resources about driving and driving cessation.

-Family member questionnaire: Questions will assess the relationship between the driver and family member, including frequency of contact and co-reliance for transportation (e.g., does older driver provide rides for family member's children, is family member available and willing to provide rides to older driver).

-Coronavirus/COVID-19 Health/Exposure Status (informed by the Coronavirus Health Impact Survey (CRISIS)): Questions will assess current impact of Coronavirus pandemic on physical and mental health, as well as other select domains (e.g., impact on important events, routine inperson activities, financial and living stability, etc).

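### The planned contamination adjustment of the longitudinal effects is not limited to baseline exposure or labelled a sensitivity analysis, so it may condition the arm effect on a post-randomization variable

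*Combined protocol and SAP*

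**What the plan says.** Analysis for Aim 1 sets the principle: "Analyses will be performed according to the principle of intention-to-treat". The same paragraph says that the longitudinal effects may be biased because controls can meet comparable messages elsewhere, and gives the remedy: "To mitigate the impact of this potential bias, we will adjust measurements of contamination as applicable".

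The measure is described under Other covariates, Driving education: "at baseline and follow-up we will assess exposure to websites, videos, courses, or other educational resources about driving and driving cessation". In Table 3 the matching row ("Use of websites, courses, or other material driving or cessation") is a covariate for hypothesis 1c only.

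The covariate sets are open. For Aim 1b: "We will adjust for baseline characteristics (gender, age, education, etc.), driving behaviors and other variables". For Aim 1c: "Also, we will adjust demographic variables and appropriate variables". Each aim has two models, GEE plus a linear mixed model for 1b and GEE plus a generalized linear mixed model for 1c, and neither is named as main.

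**The concern.** Information about driving that a participant seeks after enrollment arises after randomization. A decision aid could plausibly prompt more of it, or make it seem less necessary; the documents do not say which, if either. A model containing follow-up exposure then no longer estimates the effect of being assigned to the DDA. It removes any part of the effect that works through information-seeking, and it opens a path through unmeasured traits, such as worry about one's driving, that influence both exposure and outcome.

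The adjustment may also miss its purpose. Contamination dilutes the contrast because exposed controls move toward the DDA arm. Adding exposure as a main effect does not undo that.

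At stake is which quantity is reported for driving behavior (Aim 1c) and, if the general wording of Analysis for Aim 1 governs, for depression, regret and life space (Aim 1b). As written, the choice can be made after the data are seen.

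**Working it through.** **Which value would be used.** Contamination after enrollment can appear only in the follow-up measurement. A baseline value is harmless to the arm comparison but cannot carry out the stated mitigation. No section limits the adjustment to baseline. The sensitivity analyses that the plan does name concern missing data (Aim 1b) and the driving-evaluation recommendation (Identifying driving risk), not contamination.

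**Direction, in a linear model.** Let δ be exposure in the DDA arm minus exposure in control, and γ the within-arm coefficient of exposure on outcome. Then

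adjusted arm effect = unadjusted arm effect − γδ.

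The shift takes either sign with δ, and is zero if δ = 0 or γ = 0.

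**Illustration for Aim 1c.** The plan gives no contamination figure to reproduce, so all inputs here are assumptions. U is an unmeasured standard normal trait.

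- Exposure: logit P(C=1) = −0.85 + a·arm + k·U
- Driving reduction: logit P(Y=1) = −0.85 + d·arm + y·C + k·U
- Common-cause strength k = 1, 0.5 or 0.25

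Y is fitted on arm and C by logistic regression at population level, integrating over U, and expressed as a standardized risk difference. With a = 0.7, exposure in control and DDA is 33.1% and 46.9% at k = 1, 30.9% and 46.5% at k = 0.5, and 30.2% and 46.3% at k = 0.25. With a = −0.7 it is 33.1% and 21.4%, 30.9% and 18.6%, and 30.2% and 17.8%.

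Risk differences in percentage points, at k = 1 / 0.5 / 0.25:

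| Scenario | By arm | Adjusted for follow-up exposure |
|---|---|---|
| No DDA effect (d=0, y=0), exposure higher with DDA | 0.0 / 0.0 / 0.0 | −2.2 / −0.8 / −0.2 |
| No DDA effect (d=0, y=0), exposure lower with DDA | 0.0 / 0.0 / 0.0 | +1.9 / +0.6 / +0.2 |
| Effect only through information-seeking (d=0, y=0.8), exposure higher | 2.3 / 2.8 / 3.0 | −2.2 / −0.8 / −0.2 |
| Direct effect as well (d=0.5, y=0.8), exposure higher | 11.8 / 13.9 / 14.6 | 7.2 / 10.2 / 11.3 |

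**Equal exposure by arm (a = 0).** With d = 0.5, y = 0.8 and k = 1, the risk difference stays at 9.4 points. The odds ratio moves from 1.47 to 1.54, through non-collapsibility alone.

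**Dilution.** Set a = 0 and d = 0.6, and let exposed controls gain 0.48, which is 80% of the DDA effect. Without contamination the risk difference is 11.8 / 13.2 / 13.7 points. With contamination the intention-to-treat value is 8.4 / 9.9 / 10.4, and the adjusted value is identical. The covariate recovers none of the loss.

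**Scale.** Sample Size gives 150 per arm with 10% loss: 150 × 0.90 = 135. Near a rate of 35% (assumed), SE = √(2 × 0.35 × 0.65 / 135) = 0.058, or 5.8 points. The largest shift in the table is 11.8 − 7.2 = 4.6 points, and 4.6 / 5.8 = 0.79 SE.

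**Aim 1b.** Take a depression T-score with SD 10 (the scale's standardized value, assumed to hold here), no DDA effect, and exposure higher with the DDA. Adjustment moves 0.0 to between −0.1 and −0.6 T-score points, depending on the assumed common cause. The SE is 10 × √(2/135) = 1.2.

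**The case against.** The contamination sentence is garbled. Read literally it does not say that the DDA effect will be conditioned on follow-up exposure, and its qualifier could cover baseline exposure alone or a supplementary analysis. That stands: what is shown is an ambiguity with a natural reading, not a settled commitment.

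A reader might infer that no comparison by randomized arm survives. The documents do not support this. Aim 1b plans descriptive comparisons between the arms, and Aim 1c says "We will compare the proportion of participants who change their reported driving behaviors". What is missing is a statement of which result is the main one.

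A reader might also infer that the trial's central conclusion is exposed. It is not: the Aim 1a outcome is taken at enrollment, directly after the DDA or website. Table 3 links the exposure covariate only to Aim 1c, which is labelled exploratory.

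For Aim 1b, the word baseline can be read as governing the whole covariate list. That is possible but not clear, and Aim 1c has no such word.

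Finally, every magnitude is assumed, and the shift arises only if the DDA changes later exposure, which no section claims. This limits the weight of the point. It does not answer the equal-exposure case, where the adjustment also fails to do what it is planned for.

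**Conclusion.** The point holds as a minor one. On its natural reading the plan adjusts longitudinal arm effects for a variable measured partly after randomization, without limiting the adjustment to baseline or giving it a status. If the DDA alters information-seeking, the result departs from the declared intention-to-treat effect in a direction that cannot be known in advance. If it does not, the risk or mean difference is unchanged and dilution remains.

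The size cannot be derived from the documents. Under the assumptions above, shifts stay below one SE for both aims and show direction only. It would be wrong to conclude that the longitudinal results will be materially biased: that needs an effect of the DDA on later exposure, together with an effect of exposure on outcome or a shared cause, and the documents establish none of these.

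**What to change.** Replace the contamination sentence in Analysis for Aim 1 with:

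*The main longitudinal comparisons (Aims 1b and 1c) are by randomized arm and adjust only for covariates collected at baseline before the DDA or website is viewed, including baseline driving-education exposure and baseline driving behaviors. Follow-up exposure will be tabulated by arm and used only in a labelled sensitivity analysis.*

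In the Aim 1b and 1c paragraphs, state that the adjustment variables are baseline values, and name which of the two planned models, GEE or mixed model, gives the main result for each aim. For 1c this matters in its own right, because the marginal and subject-specific odds ratios generally differ. The plan's rule on site effects can stay as it is.

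No new data are needed: the introductory questionnaire already precedes the DDA or website (Baseline Measurements & Intervention). The cost is that dilution from contamination stays in the main estimate and is described rather than adjusted for.
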